## **7. Statistical Methods**

### **7.1. Study Subjects**

[figure not shown]
The target study population consists of post-surgical subjects of adult age at high risk of developing respiratory and cardiovascular events on the hospital ward.

#### **7.1.1. Disposition of Subjects**

Disposition of subjects will be reported following the CONSORT Flow Diagram1, even though this is a prospective, post-market interventional, pilot study and no comparisons between arms will be performed. Number of individuals at each stage of study (number of total assessed for eligibility, number of patients in FAS and number of patients in PPS) will be reported for both Capnostream™ 20p and PM1000N. Reason for not participation at each stage will be reported where known.

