## 4. Objectives and Endpoints

### 4.1. Objectives

#### 4.1.1. Primary Objective and Endpoint

The primary objective of this study is to quantify the incidence of RC markers in high risk postsurgical patients, using a system comprised of two continuous monitoring devices, connected to a remote monitoring platform.

The occurrence of at least one of the following RC markers will be considered as primary endpoint for patients monitored by Capnostream 20p during both study Phases:

1. SpO2 ≤ 90% for ≥ 3 minutes.
2. RR ≤ 8 or ≥ 22 bpm for ≥ 3 minutes.
3. etCO2 ≤ 15 or ≥ 60 mmHg for ≥ 3 minutes.
4. Apnea episode lasting > 30 seconds.

The occurrence of at least one of the following RC markers will be considered as primary endpoint for patients monitored by PM1000N-RR during both study Phases:

1. SpO2 ≤ 90% for ≥ 3 minutes.
2. RR ≤ 8 or ≥ 22 bpm for ≥ 3 minutes.

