## 5. Study Design

LIFEGUARD is a prospective, post-market interventional, pilot study. Approximately 210 patients will be enrolled in two European centers.

The study will consist of two phases. During both phases the patients will be 1:1 randomly allocated to Capnostream20p or to PM1000N-RR monitoring. The Capnostream 20p device provides data on etCO2, RR, SpO2, PR and IPI through an oral/nasal cannula and a finger sensor, while PM1000N-RR provides SpO2, PR and RR derived from plethysmography through a single finger sensor. The aim of the random allocation is to have similar patient populations receiving monitoring with the two different devices.

During the study Phase I, 70 patients will be enrolled and the alarms of both devices will be silenced and the screen information blinded, to establish the incidence of respiratory events, as is the current clinical practice in which continuous monitoring is not employed. After Phase I and before the start of study Phase II, each participating site will have a minimum of one month to familiarize themselves with the unblinded device, using a pre-defined hospital protocol for alarm management and escalation policy.

During the study Phase II, an additional 140 patients will be enrolled; but in this phase the screen information will be available, and the nursing staff will be instructed to respond to both devices' alarms based on a pre-defined hospital protocol.

During both phases, each patient will be monitored for a minimum of 24 hours and up to patient's full mobilization or for a maximum of 72 hours. At the end of the monitoring period the patient will complete the study and will continue to be treated according to standard clinical practice. Figure 1 reports the study Flow-Chart.

A survey will be conducted at the end of the study amongst the participating physicians and nurses to assess levels of their satisfaction and patient compliance with the two different monitoring technologies and the overall feasibility of continuous respiratory monitoring in a general ward setting.

[figure not shown]
Capnography and pulse oximetry monitoring device data will be collected as well as clinical data related to respiratory compromise. Patients will be monitored per standard of care.

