## 5.2 Rationale

There are few data in the literature on the incidence of RC in high risk surgical patients continuously monitored on a general ward in Europe. This pilot study will collect data on a high number of patients monitored by capnographic and/or SpO2 monitoring, thus allowing quantification of the incidence of respiratory markers and their correlation with cardiopulmonary or other complications in clinical practice and the related clinical and workflow impact.

The study will also allow evaluation of two different monitoring devices coupled with a remote patient monitoring system in terms of sensitivity and patients' compliance.

---

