## 12.3 Analysis of clinical data

Patient demographics and baseline characteristics will be presented using appropriate summary statistics. This includes mean and standard deviation, minimum, maximum and median with the interquartile range [IQR] for continuous variables and counts and percentages for categorical variables. Summary statistics will be reported with maximum 2 decimals, as appropriate. The SAS software (SAS Institute Inc., Cary, NC, USA) will be used to perform statistical analyses. Statistical tests will be based on a two-sided significance level of 0.05. Graphical representations will be used as deemed appropriate. No adjustments for multiple comparisons or multiple look at data will be performed. Outliers and influential observations will be identified via graphical plots and according to study team decision the analysis could be repeated excluding potential outliers. In case of missing data, no imputation method will be implemented for analysis.

The Full Analysis Set (FAS) will be used for primary final analysis. Any patient who does not satisfying the inclusion/exclusion criteria will be eliminate from the FAS population. Details of endpoints analyses and additional analysis will be described in the Statistical Analysis Plan. The analyses of primary objective on the proportion of patient with at least one RC markers will be reported together with their 95% confidence intervals and separately for each arm and phase of the study (see primary endpoint definition). When comparison of clinical primary outcomes is conducted the propensity score methods could be used to control for biases and confounding which may be due to the nature of this study. The

difference between the two groups within phase and between phases within groups will be analyzed by means of unpaired t-test or Mann-Whitney test according to the normal or non-normal distribution. For one secondary outcome the logistic regression model will be used to check potential predictors. Bivariate odds ratios (ORs) and 95% confidence intervals (95% CIs) will be estimated for each predictor. A multivariate logistic regression model will be performed according to univariate model's results. Other secondary outcomes will be performed using sensitivity and specificity analysis.

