## 7.2. General Methodology

For FAS and PPS descriptive statistics will be used to summarize patient characteristics. This will include mean and standard deviation, minimum, maximum and median with the interquartile range [IQR] for continuous variables and counts and percentages for categorical variables. Summary statistics will be reported with maximum 2 decimals, as appropriate. Comparisons between phases have been performed using Wilcoxon's Test for continuous variables, while comparisons of categorical variables have been performed by means of the Chi-square test or Fisher exact test for extreme proportions, as appropriate. Statistical tests were based on a two-sided significance level of 0.05.

Analysis for specific objectives have been stated in the corresponding sections (7.9.1 and 7.9.2).

When comparison of clinical primary outcomes is conducted the propensity score method could be used to control for biases and confounding which may be due to the nature of this study.

It is anticipated that SAS (SAS Institute Inc., Cary, NC, USA) will be used to perform all statistical analyses. Statistical tests will be based on a two-sided significance level of 0.05.

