## 7.9. Evaluation of Objectives

### 7.9.1. Primary Endpoint

The Primary Endpoint of the Study is to quantify the incidence of RC markers in high risk postsurgical patients, using a system comprised of two continuous monitoring devices, connected to a remote monitoring platform. The proportion and rate of “At least one RC marker” event will be calculated and reported.

The “At least one RC marker” event is defined as the occurrence of at least one of the following RC markers:

1.  $\text{SpO}_2 \leq 90\%$  for  $\geq 3$  minutes (or  $\text{SpO}_2 \leq 90\%$  for  $< 3$  min with an action taken);
2.  $\text{RR} \leq 8$  or  $\geq 22$  bpm for  $\geq 3$  minutes (or  $\text{RR} \leq 8$  or  $\geq 22$  bpm for  $< 3$  min with an action taken);
3.  $\text{EtCO}_2 \leq 15$  or  $\geq 60$  mmHg for  $\geq 3$  minutes (or  $\text{EtCO}_2 \leq 15$  or  $\geq 60$  mmHg for  $< 3$  min with an action taken);
4. Apnea episode lasting  $> 30$  seconds.

For patients monitored by PM1000N, only RC markers #1 and #2 will be considered.

RC determination will be assessed by a physician belonging to the “other” site (cross assessment by the sites). This assessment will be made by the analysis of both device and clinical data for each patient. For each patient all potential RC episodes will be derived using the Detection Tool (see Section 10.1) and will be submitted to the other site’s physician in order to adjudicate the potential RC episodes starting from episodes most likely to be RC. The adjudication will stop at the first RC occurring per patient.

The Events’ rates will be computed as (total number of “At least one RC marker” event)/(total number of time-person in PPS) and will be reported separately for each arm and phase of the study. Events’ rates will be displayed together with their 95% confidence interval (95%CI).

If the number of episode per patient result unbalanced, adjusted rates will be reported using the GEE model, together with their 95% confidence interval (95%CI).

If appropriate, also the events’ rates for each RC marker will be reported separately, for each arm and phase of the study.

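### Protocol 12.3 and SAP 7.1.1 conflict on comparing the two devices, and the by-arm primary results rest on different marker sets with no like-for-like version prespecified

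*SAP*

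**What the plan says.** Protocol 8.6 randomises patients 1:1 to device in each phase, stratified by centre. Protocol 5 gives the purpose: "The aim of the random allocation is to have similar patient populations receiving monitoring with the two different devices". Protocol 5.2 adds: "The study will also allow evaluation of two different monitoring devices coupled with a remote patient monitoring system in terms of sensitivity", and that sentence goes on to name patient compliance as well.

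On analysis, protocol 12.3 states that the "difference between the two groups within phase and between phases within groups will be analyzed by means of unpaired t-test or Mann-Whitney test", the choice depending on normality. It names no endpoint for this.

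SAP 7.1.1 presents patient disposition in CONSORT form "even though this is a prospective, post-market interventional, pilot study and no comparisons between arms will be performed". SAP 7.2 is worded to match: "Comparisons between phases have been performed using Wilcoxon's Test for continuous variables", with Chi-square or Fisher tests for categorical variables. SAP 7.6 and 7.9.2 likewise name only phase comparisons.

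On the endpoint, protocol 4.1.1 and SAP 4.1 give Capnostream patients four qualifying markers: SpO2, RR, etCO2 and "Apnea episode lasting > 30 seconds". SAP 7.9.1 then says: "For patients monitored by PM1000N, only RC markers #1 and #2 will be considered". The same section reports rates with 95% CIs for each arm and phase, and single-marker rates by arm and phase only where judged appropriate.

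**The concern.** An analyst cannot follow both documents. One calls for a within-phase device analysis and the other rules it out. The SAP says that it is based on protocol 2.0 and was updated to align with it, yet its section on changes to the planned analysis (7.12) covers only the 24-hour and 90% cut-offs. Protocol 12.2 requires departures to be described and justified in the final report, so the gap will surface there if it is not closed now.

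The second problem concerns how the results will read. Device is the only randomised factor, since the phases run one after the other. The report will show a Capnostream figure and a PM1000N figure for each phase, both labelled as the primary endpoint, although one counts four kinds of event and the other two. Part of any gap is then definition rather than patients or device performance, and nothing planned separates the two reliably.

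**Working it through.** **1. The plan's own figure.** SAP 6 sizes the study for one proportion: 10%, precision 5 points, 95% confidence, probability at least 0.80 of reaching that precision. With exact (Clopper-Pearson) intervals the smallest n is 179. At the stated 182 the probability is 0.855, and 182 × 1.15 = 209.3, about 210. The figure is reproduced to within 3 patients. It contains no between-arm element, so the documents give no planned effect size or precision for a device contrast.

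**2. Size of the definitional gap.** Let s be the proportion with an SpO2 or RR marker, assumed equal in both arms. Let e be the share of the remaining Capnostream patients caught only by etCO2 or apnea. The Capnostream composite is s + (1 − s)e, the PM1000N composite is s, and the gap is (1 − s)e. Neither s nor e is in the documents, so these are assumed values:

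| s | e = 10% | e = 30% | e = 50% |
|---|---|---|---|
| 10% | 19% v 10% | 37% v 10% | 55% v 10% |
| 30% | 37% v 30% | 51% v 30% | 65% v 30% |
| 50% | 55% v 50% | 65% v 50% | 75% v 50% |

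The gap runs from 5 to 45 points with no difference on the shared markers. A reader who tested the two Phase II figures (70 per arm, no dropout, two-sided 0.05) could be misled. For 51% v 30%, with pooled proportion 0.405:

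- critical difference = 1.96 × √(2 × 0.405 × 0.595 / 70) = 0.163
- standard error under the alternative = √((0.51 × 0.49 + 0.30 × 0.70) / 70) = 0.081
- chance of significance = Φ((0.21 − 0.163) / 0.081), about 72%

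At s = 30% the same calculation gives 14% for e = 10% and 99% for e = 50%.

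**3. Whether the planned output already allows a like-for-like reading.** Single-marker rates by arm are conditional, and they are not a combined SpO2-or-RR proportion. Under SAP 7.9.1 a physician at the other site adjudicates candidate episodes, beginning with those most likely to be RC, and stops at the first one confirmed. A Capnostream patient confirmed on etCO2 or apnea may never have the SpO2 or RR episodes adjudicated. The shared endpoint may therefore not be recoverable from adjudicated data. The Detection Tool (SAP 10.1) finds all candidate episodes in both arms before adjudication, so its output can supply the endpoint.

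**4. Precision of a shared-marker risk difference.** Enrolled per arm: 35 in Phase I and 70 in Phase II. Applying the plan's 10% and 5% losses additively, 35 × 0.85 = 29.75 and 70 × 0.85 = 59.5, taken as 30 and 60. Half-width = 1.96 × √(2p(1 − p)/n):

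| Incidence p | Phase I, n = 30 | Phase II, n = 60 |
|---|---|---|
| 50% | 1.96 × √(0.50/30) = 25.3 points | 1.96 × √(0.50/60) = 17.9 points |
| 10% | 1.96 × √(0.18/30) = 15.2 points | 1.96 × √(0.18/60) = 10.7 points |

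**The case against.** The best defence is that no listed objective asks for a device contrast. The comparisons in protocol 4.1.2 and SAP 4.2 are between phases, and randomisation is explained as a way to obtain similar populations. The protocol 12.3 sentence names no endpoint and its tests do not fit a binary one, so it is not clearly a planned test of the primary outcome. Protocol 12.3 also leaves endpoint detail to the SAP. The unequal marker sets are stated openly and follow from what each device measures. All of this stands, and it means that the absence of a powered arm test in a precision-based pilot is not an error.

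A reader might infer that the SAP makes the randomisation worthless. The documents do not support that: by-arm rates with CIs are planned for each phase, single-marker rates are foreseen, and SpO2 and RR are in both definitions.

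A reader might also infer that the Capnostream figure must be the higher one. That holds only for the same patients with identical readings. RR comes from capnography in one arm and plethysmography in the other, so the shared markers could differ in either direction.

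Nor is a clean contrast available at no cost. The PPS needs 24 hours of effective monitoring, which depends partly on tolerating a cannula used in one arm only. In Phase II the recommended alarms in protocol Appendix B include etCO2, apnea and IPI, which PM1000N does not supply, so a device difference means something different in each phase.

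None of this removes the contradiction between protocol 12.3 and SAP 7.1.1, or the absence of a prespecified like-for-like figure.

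**Conclusion.** The point holds as a matter of consistency and interpretability; it does not show that the design fails. The protocol and SAP give opposite instructions on within-phase device comparison, and the SAP does not record the departure. The by-arm primary composites are not comparable as defined. The size of the distortion is unknown from the documents: between 5 and 45 points over the assumed ranges above, and close to zero if few Capnostream patients qualify on etCO2 or apnea alone. A shared-marker estimate would be descriptive only. Its interval widths rest on the assumed 30 and 60 evaluable patients per arm and an incidence of 10% to 50%. The change should be made, and it is easiest to make before adjudication and analysis begin.

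**What to change.** 1. Reconcile protocol 12.3 with SAP 7.1.1, and record the outcome in SAP 7.12.
2. In SAP 7.9.1, label the four-marker composite as Capnostream-only.
3. Add a descriptive composite of markers #1 and #2 for both arms, derived from Detection Tool output in both. State whether it includes the SAP's limb for shorter episodes with an action taken, since that limb needs clinical data as well as device data.
4. In place of the t-test or Mann-Whitney test, report the Capnostream minus PM1000N risk difference with 95% CI separately for each phase, in the FAS as well as the PPS. Do not rely on an estimate pooled over phases, because the Phase II alarms differ by device.
5. State that RR is measured by different methods in the two arms, and show SpO2 alone as the cleanest shared marker.

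The cost is a derived endpoint and a few table rows. The shared composite would be unadjudicated, its RR part would mix measuring methods, and its intervals would be wide. Extending adjudication to the first shared-marker episode would remove the first drawback but adds work at both sites.

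If the sponsor wants no device contrast, the smaller change is to amend protocol 12.3 and state beside the by-arm results that the definitions differ.

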**Table 2 - Number of Subject Screened and Enrollments by Site and Ward**

**Figure 2 – CONSORT Flow diagram of Patient Disposition**

### 7.1.2. Clinical Investigation Plan (CIP) Deviations

Deviations are instance(s) of failure to follow, intentionally or unintentionally, the requirements of the CIP. Intentional deviations are not permitted, except where necessary to protect the life or physical well-being of a subject in an emergency situation. All deviations must be documented and explained, regardless of the reason for the deviation. Deviations will be documented on the Protocol Deviation eCRF, with the associated visit of the deviation, the type of the deviation and the reason for the deviation.

All Deviations will be reviewed and classified by the clinical study team and the following tables will describe study deviations.

**Table 3 - Protocol Deviation by Reason - FAS**

**Table 4 - Protocol Deviation by Visit - FAS**

**Listing 1 - Other deviations – FAS**

### 7.1.3. Analysis Sets

The following patient sets will be used for the analysis:

- The Full Analysis Set (FAS) includes all patients actively enrolled in the study, who signed Informed Consent Form (ICF), fulfilled the inclusion/exclusion criteria and monitored by CS20p or PM1000N. The FAS will be used to describe both baseline characteristics and safety outcomes of the study population;
- The Per Protocol Set (PPS) includes all patients in the FAS, without major protocol deviations, who have at least 24 hours of monitoring *effective time*. The PPS will be used to describe baseline characteristics of the study population and to evaluate the primary and secondary endpoints. Patient with poor quality of device data, defined as having less than 90% of time continuously monitored, will be included or excluded from the PPS, as appropriate.

The following table shows how each population set will be used for analyses:

Population set	Baseline assessment	Primary and Secondary Endpoint #1	Secondary Endpoints #2, #3, #4 and #5	Safety AE Death
FAS	✓		✓	✓
PPS	✓	✓	✓	

For those patients who have less than 24 hours or poor quality of device data monitoring or who withdrew, the analyses will include all data up to the point of their last data collection only for FAS population.

An additional set could be created during the analysis phase, in case necessary to investigate on a particular subgroup of patients.

 Effective time is the cumulative time with valid recorded data. This aimed to filter out periods of time where the patient was not connected to the Capnography cannula or pulse-ox sensor, but recording was on-going (the patient was not monitored during this time).

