## 8.12 Patient Withdrawal or Discontinuation

If a patient is withdrawn from the clinical study, the reason for withdrawal shall be recorded on the Study Exit eCRF and in the patient's medical record.

Possible reasons for withdrawal from the study are:

- Adverse Event;
- Patient withdrew consent;
- Investigator withdrew patient from the study for medical reasons;
- Investigator withdrew patient from the study due to inclusion/exclusion criteria not met.

No patient follow-up is scheduled as per study design (excluding resolution of ongoing adverse events). Patients withdrawn for reasons other than screen failure will not be replaced.

Withdrawn patients will be treated according to standard clinical practice.

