## 7.10. Safety Evaluation

Adverse events in the Full Analysis Set will be presented in summary tables and supporting data listings. Secondary objectives described in Section 7.9.2 include safety evaluations and will be summarized as already described.

Adverse events will be presented using the MedDRA coding and with the following summary tables and supporting data listing:

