**Table 15 – Adverse Event by Primary System Organ Class and Preferred Term – FAS**

**Table 16 - Adverse Event Seriousness and Relatedness – FAS**

**Table 17 - Individual Adverse Events for which Sponsor and Investigator disagreed – FAS**

**Listing 2 - Individual Adverse Events – FAS**

**Table 18 - Death Summary – FAS**

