**Listing 3 - Death – FAS**

## **7.11. Health Outcomes Analyses**

No specific health outcomes' analyses were planned in the protocol, except for those considered in the secondary objectives.

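### All planned adverse event and death outputs use an FAS limited to eligible patients, so a patient who was monitored and later ruled ineligible is missing from them

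*SAP*

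**What the plan says.** SAP 7.1.3 sets three conditions for the FAS: signed consent, eligibility and monitoring. The eligibility and monitoring conditions, and the use of the set for safety, read: "fulfilled the inclusion/exclusion criteria and monitored by CS20p or PM1000N. The FAS will be used to describe both baseline characteristics and safety outcomes". The table of populations in that section assigns adverse events and deaths to the FAS alone. The only other defined set, the PPS, is a subset of the FAS.

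Protocol 12.3 applies the same rule as a removal: "Any patient who does not satisfying the inclusion/exclusion criteria will be eliminate from the FAS population".

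SAP 7.10 states: "Adverse events in the Full Analysis Set will be presented in summary tables and supporting data listings". The output titles agree, for example "Listing 2 - Individual Adverse Events – FAS", "Table 18 - Death Summary – FAS" and "Listing 3 - Death – FAS". The deviation outputs listed after SAP 7.1.2 carry the same label, for example "Table 3 - Protocol Deviation by Reason - FAS".

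Among the possible reasons for withdrawal, Protocol 8.12 gives: "Investigator withdrew patient from the study due to inclusion/exclusion criteria not met".

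**The concern.** Safety reporting normally follows exposure: a patient who wore the device counts, whether or not he or she should have been enrolled. Here eligibility is a condition of entry to the only set used for safety. A serious event or death in a monitored patient who is later ruled ineligible would appear in no planned table or listing. The eligibility violation would also be missing from the deviation outputs, which use the same set, so a reader of those outputs would have no sign of the omission.

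One exclusion criterion also overlaps with device harms. Exclusion 4 in Protocol 7.4 names intolerance of the capnography cannula and skin allergy to medical adhesives. Protocol Appendix A, Table 6 lists sensor- or cannula-site discomfort and allergic reaction as anticipated device-related events. The same occurrence could be both the harm and the ground for removal. Because only Capnostream uses the cannula (Protocol 5), removal for cannula intolerance could differ between the randomised devices.

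**Working it through.** The point concerns a definition. The plan gives no figure to reproduce, so the check is mainly a cross-reading.

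**Step 1. Can a monitored patient be found ineligible?** Protocol 8.2 limits screen failure to patients who fail the criteria before ward monitoring. Protocol 8.12 lists unmet criteria as a withdrawal reason with no such time limit. Some withdrawals under that reason may be screen failures who never wore a monitor, but the reason is not confined to them. Enrolment already requires the criteria to be met (Protocol 7.2 and 8.5), so the removal rule in Protocol 12.3 matters mainly for rulings made later.

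**Step 2. Does another provision bring such a patient back?**
- SAP 7.1.3 keeps data up to last collection for withdrawn patients, but only within the FAS.
- SAP 7.1.3 allows an additional set, but it is optional, undefined and meant for subgroups.
- SAP 7.1.1 reports reasons for non-participation where known. That could show the removal but not the event.
- Secondary endpoint #2 (respiratory AEs, SAEs, ICU transfers, Code blues, RRT responses) uses the FAS and PPS, so the comparison between phases has the same gap.

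None of these restores the patient to the safety outputs.

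**Step 3. Illustration of size.** The only input from the documents is planned enrolment of about 210 (SAP 6). The number removed, k, and the risk q that a removed patient had at least one reportable event are assumptions. Treating patients as independent:

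P(at least one patient with an event is omitted) = 1 - (1 - q)^k

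| Assumed removal | k | q = 5% | q = 25% |
|---|---|---|---|
| 1% | 2 | 1 - 0.95^2 = 10% | 1 - 0.75^2 = 44% |
| 2% | 4 | 1 - 0.95^4 = 19% | 1 - 0.75^4 = 68% |
| 5% | 10 | 1 - 0.95^10 = 40% | 1 - 0.75^10 = 94% |

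The products are 2.1, 4.2 and 10.5 patients, taken as 2, 4 and 10. The 25% column would be relevant only if removals tended to be prompted by the device reaction itself.

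**Step 4. Effect on a reported proportion, also with assumed counts.** Five device events in 210 patients is 5/210 = 2.38%. If 4 patients are removed, 2 of them with an event, the report shows 3/206 = 1.46%. In the extreme case of 2 reactions in 210 (1.0%, exact 95% CI 0.1% to 3.4%) with both patients removed, the report shows 0/208, with upper limit 1 - 0.025^(1/208) = 1.8%.

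**The case against.** The strongest reply is that little is lost in practice. Adverse events go on the AE eCRF (Protocol 10.2), serious events and device effects go to the sponsor immediately (Protocol Table 4), deaths must be reported (Protocol 10.3), and every deviation is documented (Protocol 8.11). This stands. A reader might infer that harms vanish from the study record, and the documents do not support that. What is missing is their place in the planned tables and listings.

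A second reply concerns device reactions. A reader might infer that sensor allergies will be reclassified as ineligibility and that device harms will therefore be understated. The documents do not support that either. Eligibility is assessed at screening (Protocol Table 2). Protocol 9.1 and Table 6 describe the adhesive criterion in terms of known allergies. A new reaction is an anticipated device event, and Protocol 8.12 lists an adverse event as a separate withdrawal reason. The natural route for such a patient is withdrawal with the event still in the FAS. However, exclusion 4 itself does not say the allergy must be known, so removal remains possible, though not automatic.

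A third reply is that Protocol 8.12 lists only possible reasons and predicts no such withdrawals. That is also right: the text allows them and gives no frequency.

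None of these replies changes the set definition, which on its own terms excludes a monitored patient found ineligible.

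**Conclusion.** The concern holds for the planned outputs. By the wording of SAP 7.1.3 and Protocol 12.3, a monitored patient later ruled ineligible is left out of Tables 15-18, Listings 2-3 and the deviation outputs, and no exposure-based set exists to include that patient. Confidence in this reading is high.

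The size is unknown, because the documents give neither a rate of ineligibility found after monitoring starts nor an event risk. The 10% to 40% range (44% to 94% at the higher assumed risk) and the shifts in reported proportions show only that a few removals could matter when event counts are small. They should not be read as estimates of bias. The change is worth making before analysis because the rule is explicit, the remedy is small and the data are already being collected.

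**What to change.** In SAP 7.1.3, define a Safety Set: every consented patient connected to a study monitor, whatever the later eligibility ruling or deviations, analysed by device worn and by phase. Use it for:

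- Tables 15-18 and Listings 2-3;
- the deviation outputs (Tables 3-4 and Listing 1);
- the safety components of secondary endpoint #2, so that event counts in SAP 7.9.2 and 7.10 agree.

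Update the population table in SAP 7.1.3, the first sentence of SAP 7.10 and the output titles to match. Leave the sets for the primary endpoint and the other secondary endpoints as they are. Protocol 12.3 ties the FAS to the primary analysis and names no safety population, so its FAS definition can stand.

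The cost is SAP wording and one population flag, with no new data. Adverse event counts may be slightly less favourable.
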